#### 4.2 Scientific Rationale for Study Design

We chose to randomize at the school level as opposed to the individual level for several reasons. We view PLANTS as an intervention that can be implemented within schools as a whole to foster more inclusive, supportive, affirming, and protective environments for SGMY. We also minimize contamination amongst school staff by randomizing at school versus individual levels. By randomizing at the school level, we can estimate the impact that the intervention has had on all youth within a school by leveraging existing surveillance data that assesses censuses of students (such as the MetroWest Adolescent Health Survey). By leveraging existing health surveillance infrastructures, our study will yield large sample sizes and high statistical power for finding health-promoting effects at the individual level.

The comparison group selection was challenging because there is no gold standard for improving schoolbased environments for SGMY by changing behaviors of high school staff. Nevertheless, we decided to select a practical alternative to the PLANTS intervention; therefore, the active control materials will be freely available online courses that aim to improve SGMY school environments. Note that this is an active control intervention, therefore all participants in this group are expected to receive training in the primary outcomes of the PLANTS interventions. Compared to using a placebo or pure control, our ability to find differences between these the study harms is somewhat hampered. However, we believe using an active control arm is more ethical given the minimal risks of participation in such online trainings plus their potential impact for bolstering environments for SGMY well-being.

#### 4.3 Justification for Intervention

We decided to deliver PLANTS using an online design because this model is more scalable than traditional inperson trainings, thereby reaching more people. We include both synchronous and asynchronous modules, as there is evidence that both is better than asynchronous training only. The length of the intervention evolved throughout the development of the project with feedback from the community. The number of asynchronous elements were identified through our intervention mapping process and by chunking PLANTS' performance objectives into complementary components. The lengths of videos were determined based on expertise provided by teaching and learning experts. Because this is a pilot study including intervention adherence, a participant will have to complete at least one item in the PLANTS intervention to have evaluable data.

### 4.4 End-of-Study Definition

A participant is considered to have completed the study if they have completed the baseline and follow-up surveys. The post-intervention interview is optional and will be conducted with a sub-sample of the study participants.

The end of the study is defined as completion of the follow-up survey or completion of the staff follow-up interview, as shown in the Schedule of Activities.

# 5 STUDY POPULATION

# 5.1 Inclusion Criteria

# School Inclusion Criteria:

To be eligible to participate in this study, schools must meet all of the following criteria:

- Participated in the 2021 MetroWest Adolescent Health Survey (MWAHS)
- Plan to participate in the 2023 MWAHS
- Grant us permission to access their MWAHS data
- Willing and able to provide emails addresses for all school staff
- Willing and able to provide us a letter of support denoting their participation in our study

#### Staff Inclusion Criteria:

To be eligible to participate in this study, staff must meet all of the following criteria:

- Currently employed by an enrolled school in the MetroWest Region of Boston, Massachusetts
- Age 18 years old or older
- Consents to participate

#### 5.2 Exclusion Criteria

#### School Exclusion Criteria:

N/A

#### Staff Exclusion Criteria:

An individual who meets any of the following criteria will be excluded from participation in this study:

• Does not interact with high school students at work

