# PLANTS Pilot Trial Protocol STUDY21080178 1 PROTOCOL SUMMARY

#### **Synopsis** 1.1

Title	Draviding LODTO, Adalassanta with Numberson Tructure thisses, and Osfette
Title:	Providing LGBTQ+ Adolescents with Nurturance, Trustworthiness, and Safety (PLANTS): Pilot Cluster-Randomized Controlled Trial
Grant Number:	K01AA027564
Study Description:	This pilot cluster-randomized controlled trial will evaluate the PLANTS (Providing LGBTQ+ Adolescents with Nurturance, Trustworthiness, and Safety) course among high school staff. The primary hypotheses are that the PLANTS course will have high acceptability, usability, appropriateness, and feasibility as reported by high school staff.
Objectives:	
 
Primary Objective: 
 
For high school staff, is PLANTS acceptable, usable, appropriate, and feasible?
 
Secondary Objectives: 
 
To what extent was the PLANTS course and trial successfully implemented and safe for high school staff and schools?
 
Among high school staff participants in the PLANTS arm, do they report pre-post improvements in active-empathic listening, self-efficacy for supporting, affirming,
 
 
 
 
 

	and protecting sexual and gender minority youths, and positive bystander intervention behaviors for bullying? -Among high school staff, is the PLANTS intervention more efficacious in improving their active-empathic listening, self-efficacy for supporting, affirming, and protecting SGMY, and positive bystander intervention behaviors for bullying than an email intervention of publicly available resources?
Endpoints:	Primary Endpoints: Intervention acceptability, usability, appropriateness, and feasibility. Secondary Endpoints: Intervention efficacy for school staff; Success of intervention implementation; Success of trial implementation; Intervention safety.
Study Population:	The primary study population is high school staff, aged 18 years old and over, who work at high schools in the MetroWest Region outside Boston, Massachusetts.
Phase or Stage:	Pilot Phase
Description of Sites Enrolling Participants:	This is a single site study conducted by the University of Pittsburgh.
Description of Study	The PLANTS (Providing LGBTQ+ Adolescents with Nurturance, Trustworthiness,

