#### Study Intervention: PLANTS Course

The intervention being studied, PLANTS (Providing LGBTQ+ Adolescents with Nurturance, Trustworthiness, and Safety), is an online-delivered training program, including asynchronous and synchronous activities targeting high school staff. This intervention is informed by the Information-Motivation-Behavior theory to target high school staffs' skills, self-efficacy, knowledge, and outcome expectations. Members of the study population as well as collaborators invested in SGMY well-being provided valuable feedback on PLANTS throughout its development.

Regarding the intervention's targeted behavioral outcomes, upon completion of the PLANTS program, high school staff will: provide interpersonal support and affirmation to SGMY; provide educational resources that are inclusive of SGMY; provide safe spaces for SGMY; promote acceptance of SGMY among cisgender heterosexual youth; prevent and reduce bullying, cyberbullying, and harassment of SGMY; evaluate and advocate for SGMY inclusivity and protections in school policies; and maintain the confidentiality of SGMY. By having high school staff achieve these behavioral outcomes, we hypothesize that SGMY will experience less

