#### PLANTS Course: Providing LGBTQ+ Adolescents with Nurturance, Trustworthiness, and Safety

This intervention, PLANTS Course, is an online training program for high school staff. The behavioral outcomes of PLANTS are to train high school staff to: provide interpersonal support and affirmation to SGMY; support LGBTQ+ students in meeting their basic needs; provide educational resources that are inclusive of LGBTQ+ students; provide safe spaces for LGBTQ+ students; promote acceptance of LGBTQ+ students among non-LGBTQ+ students; prevent and reduce bullying, cyberbullying, and harassment of LGBTQ+ students; evaluate and advocate for LGBTQ+ inclusivity and protections in school policies; and maintain the confidentiality of LGBTQ+ students. To achieve these outcomes, we harnessed Information-Motivation-Behavior theory to target high school staff's skills, self-efficacy, knowledge, and outcome expectations. PLANTS uses asynchronous and synchronous online activities with 3 primary sections: Trustworthiness, Safety, and Nurturance. Each section includes, as asynchronous activities, recorded presentations, student testimonials, activities, and downloadable resources for future reference. There are required synchronous Live Zoom Events delivered via Zoom that are 1.5 hours each. Live Zoom Events will be moderated by a trained interventionist and will be tailored to the need of participants. Three Live Zoom Event are offered and participants are required to complete all three. Sections are opened once a month for ~3 months. The modules were developed by my research team, including undergraduate students and graduate students with a variety of academic backgrounds, in partnership with high school staff and other professionals specialize in LGBTQ+ youth or education. We use Canvas Learning Management Software to deliver PLANTS. We will monitor intervention compliance and fidelity via module guestionnaires, Canvas informatics, event attendance, and follow-up survey questionnaires.

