# Staff Screener (Time 0)

- 1. Inclusion/exclusion will be self-administered via REDCap by high school staff. These are the exact questions:
  - a. Which schools do you currently work at? [drop down list of MetroWest Schools + "Somewhere else" + write-in]
  - b. How often do you interact with students at your job? [0: Daily; 1: Weekly; 2: Monthly; 3: Yearly; 4: Never]
  - c. How old are you? [integer validation]
- 2. Informed consent: We will provide informed consent materials online via REDCap.

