#### 9.3 Populations for Analyses

We will analyze data from the following populations:

- PLANTS Primary Endpoint Population: This includes all participants who were in the PLANTS study arm and have AIM, IAM, or FIM data as reported in the follow-up survey.
- Intention-to-Treat (ITT) Analysis Population: This includes all staff participants who enroll in the study.
- Per-Protocol Analysis Population: This includes all staff participants who enroll in the study.
- PLANTS Condition Population: Staff participants in the PLANTS arm.
- EMAILS Condition Population: Staff participants in the PLANTS arm.
- Qualitative Interview Population: Staff who participate in interviews.

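### Staff who gave input on PLANTS while it was being developed are neither excluded nor identified, so the trial cannot show that its primary ratings come from people independent of the course

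*Combined protocol and SAP*

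**What the plan says.** On who shaped the course, section 2.1 (Study Intervention: PLANTS Course) states: "Members of the study population as well as collaborators invested in SGMY well-being provided valuable feedback on PLANTS throughout its development". Section 6.1.1 adds that the research team built the modules "in partnership with high school staff and other professionals specialize in LGBTQ+ youth or education". The synopsis (1.1) defines the population: "The primary study population is high school staff, aged 18 years old and over, who work at high schools in the MetroWest Region".

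On who may enrol, section 5.1 asks for three things of staff: "Currently employed by an enrolled school in the MetroWest Region of Boston, Massachusetts", age 18 or over, and consent. The single staff exclusion in 5.2 is "Does not interact with high school students at work". School exclusions are marked N/A, so a school whose staff contributed may itself enrol. Recruitment (5.5) is a census of student-facing staff at the enrolled schools.

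On identification, the Staff Screener (Time 0) in 8.1 has three questions: current school, "How often do you interact with students at your job", and age. The baseline survey records previous professional development on working with SGMY, but that item is generic and would not single out someone who had reviewed PLANTS.

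On analysis, 9.3 defines the PLANTS Primary Endpoint Population thus: "This includes all participants who were in the PLANTS study arm and have AIM, IAM, or FIM data as reported in the follow-up survey". The ITT population is everyone who enrols. Section 9.4.2 reports the primary endpoints as means with 95% CIs against fixed benchmarks. Neither the bias assessments in 9.4.3 nor the subgroup list in 9.4.7 mentions involvement in development.

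**The concern.** Read together, 2.1 and 1.1 place people who influenced the course in the regional pool from which the trial recruits, and nothing later in the plan filters or flags them.

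This matters most for the primary endpoints. They are self-ratings of the course, given unblinded, averaged without adjustment and compared with a fixed threshold rather than with another arm. A tilt in who does the rating passes straight into the result, because no comparator can cancel it. The protocol already names social desirability bias as a risk of the unblinded design (4.1, 6.3). A person rating a course that reflects their own suggestions is a natural example of that risk.

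A second, weaker consequence concerns the EMAILS arm. A contributor at an EMAILS school would be analysed as a control despite earlier contact with PLANTS content. Section 4.2 gives reduced contamination among school staff as one reason for randomising schools, but randomisation cannot undo exposure that came before it.

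**Working it through.** **1. Can a contributor pass from development into the primary means?**

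- Pool: 2.1 says contributors included members of the study population, and 1.1 says that population is MetroWest high school staff.
- Invitation: 5.5 invites all student-facing staff at an enrolled school.
- Eligibility: 5.1 and 5.2 contain nothing on prior involvement.
- Screening: none of the three Time 0 questions asks about it.
- Analysis: 9.3 takes every PLANTS-arm participant with AIM, IAM or FIM data.

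No step stops or marks the contributor. The text does not establish that any contributor works at one of the four schools.

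**2. The plan's own sample size (9.2).**

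86 per school × 4 schools = 344 invited; × 0.50 = 172 consenting; × 0.50 = 86 in the PLANTS arm; × 0.75 = 64.5, which rounds to the stated 65. The figure reproduces.

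**3. Shift in a primary mean.**

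If k of 65 raters score on average d points above the rest, the mean moves by (k/65) × d. The documents give neither k nor d, so both are assumptions.

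| k | d = 0.5 | d = 1.0 | d = 1.25 |
|---|---|---|---|
| 1 | 0.008 | 0.015 | 0.019 |
| 3 | 0.023 | 0.046 | 0.058 |
| 5 | 0.038 | 0.077 | 0.096 |
| 10 | 0.077 | 0.154 | 0.192 |

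With k = 0 the shift is zero.

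**4. When the shift could change the conclusion.**

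The benchmark for AIM, IAM and FIM is a mean above 3.75. If the other 62 raters averaged 3.70 and three contributors averaged 4.8, the pooled mean would be (3 × 4.8 + 62 × 3.70)/65 = 243.8/65 = 3.751, just over the line. At the extreme, if five contributors gave the maximum of 5, the pooled mean would reach 3.75 with the other 60 averaging only (65 × 3.75 − 5 × 5)/60 = 218.75/60 = 3.65.

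For scale, 9.2 expects a 95% CI width of at most 0.33, a half-width of 0.165. The three-rater shift of 0.051 is under a third of that half-width.

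No SUS example is given, because the SUS benchmark is above 70 in 9.1 and above 75 in 9.4.2. Those two sections need reconciling first.

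**5. Cost in precision of leaving contributors out.**

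Width scales with 1/√n. Removing five raters takes 0.33 to 0.33 × √(65/60) = 0.34.

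**6. EMAILS arm.**

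Section 9.4.3 tests group × time, which is change from baseline compared between arms. Exposure before baseline may already be reflected in the baseline score, may leave less room for change, and may occur in either arm. No direction follows from the documents. If 5 of 65 control completers had been exposed, that would be 7.7% of them.

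**The case against.** The best reply is that the overlap is inferred. Section 6.1.1 names no region for the high school staff it mentions. Section 2.1, read with the synopsis, reaches the MetroWest Region but not the four enrolled schools. This stands, and it is why the size of the problem cannot be fixed and may be nil.

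Three stronger readings are tempting, and the documents do not support them:

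- **That co-developers will be rating their own course.** The text speaks of feedback and partnership. It does not say how many staff took part, how much material they saw, or whether any will enrol. It also describes no earlier testing of PLANTS among staff.
- **That contributors' ratings necessarily push the means up.** An upward tilt is plausible, but the documents hold no evidence on how contributors rate the course.
- **That the group × time comparison is contaminated in a known direction.** The contamination remark in 4.2 concerns staff sharing a school, and the model measures change from baseline.

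It can also be said that the worked example sits close to the benchmark and that its shift is small beside the planned interval. That is fair: the shift matters only when a mean lands near 3.75.

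Finally, a census of staff is deliberate, and 4.2 presents PLANTS as something a whole school takes up. Keeping every eligible person in a descriptive pilot is defensible, which weakens the case for outright exclusion. It does not weaken the case for asking the question, since without it the trial could not tell readers whether its raters were independent.

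**Conclusion.** The gap is real: eligibility, screening and the analysis populations all leave staff who had a hand in developing PLANTS unidentified, although the protocol says such people belong to its study population. Whether any will be among the raters is not stated.

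Under the assumption of 1 to 10 such raters among 65, scoring 0.5 to 1.25 points higher, an AIM, IAM or FIM mean moves by about 0.01 to 0.19. That can carry a mean across 3.75 only if it is already close. For the secondary comparison, the EMAILS group becomes less clean, by an unknown amount and in an uncertain direction.

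This is an inexpensive safeguard for the headline result. It is not evidence that the result will be biased.

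**What to change.** 1. Add one yes/no item to the Time 0 screener in 8.1, asking whether the person has been involved in developing or reviewing PLANTS.
2. State in 9.3 and 9.4 that the four primary means with their 95% CIs, and the group × time models, will also be reported without staff who answer yes. Report how many answered yes in each arm.
3. If the sponsor prefers, exclude these staff in 5.2 instead. Flagging keeps the census intact and is easier to defend. It also remains workable if recruitment has already begun.

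The cost is one question, a small additional analysis and slightly wider intervals in that analysis (about 0.33 to 0.34 if five raters are left out). Exclusion would also lose a few willing participants.

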# Version 1.0 2024.04.05

### 5.3 Lifestyle Considerations

#### N/A

#### 5.4 Screen Failures

Individuals who do not meet the criteria for participation in this trial (screen failure) are unlikely to meet them within the study window and will not be rescreened.

#### 5.5 Strategies for Recruitment and Retention

#### School Staff

**Recruitment.** For high schools to be eligible to enroll in our study, school administrators must be willing to provide email addresses for all school staff members so that we can adequately recruit all staff in the high school. At the enrolled high schools, we will administer online surveys via REDCap to all staff members that interact with students (e.g., a census of teachers, administrators, nurses, counselors). We will email participants a screener survey to confirm their eligibility for participation, a consent form, and a baseline survey. We will also place study advertisements in their school mailboxes.

**Retention.** The follow-up survey will be delivered post-intervention. Several methods used by [name] and his mentorship team have proven valuable in retention of participants in longitudinal studies. To keep participants engaged, we will: inform participants at the beginning about the anticipated time burden and associated incentives; provide participants with clear instructions about their tasks; send personalized reminder emails and text messages to participants who have not completed a survey; email participants 1 day in advance of their survey, reminding them to look out for the upcoming survey email and to check spam filters; encourage participants to reach out to us when they have questions or concerns via email, phone, or text; and provide participants with escalating incentives that increase each survey. We will monitor retention on a weekly basis and more frequently if needed to ensure we are maintaining high retention.

**Incentives.** To incentivize school staff to complete the baseline survey, we will provide \$20 gift cards to each participant and will raffle \$30 gift cards to 20% of participants who take the baseline survey within each school. To incentivize school staff to complete the follow-up survey, we will provide \$30 gift cards to each participant who completes the survey will and raffle \$40 gift cards to 20% of participants who take the follow-up survey within each school. For staff who complete the follow-up interview, we will provide \$50 incentive as a thank you for their time.

# 6 STUDY INTERVENTIONS

#### 6.1 Study Intervention Administrations

#### 6.1.1 Study Intervention Descriptions

We have two study conditions, intervention and active control. We describe each condition using the TIDieR Checklist.

#### PLANTS Course: Providing LGBTQ+ Adolescents with Nurturance, Trustworthiness, and Safety

This intervention, PLANTS Course, is an online training program for high school staff. The behavioral outcomes of PLANTS are to train high school staff to: provide interpersonal support and affirmation to SGMY; support LGBTQ+ students in meeting their basic needs; provide educational resources that are inclusive of LGBTQ+ students; provide safe spaces for LGBTQ+ students; promote acceptance of LGBTQ+ students among non-LGBTQ+ students; prevent and reduce bullying, cyberbullying, and harassment of LGBTQ+ students; evaluate and advocate for LGBTQ+ inclusivity and protections in school policies; and maintain the confidentiality of LGBTQ+ students. To achieve these outcomes, we harnessed Information-Motivation-Behavior theory to target high school staff's skills, self-efficacy, knowledge, and outcome expectations. PLANTS uses asynchronous and synchronous online activities with 3 primary sections: Trustworthiness, Safety, and Nurturance. Each section includes, as asynchronous activities, recorded presentations, student testimonials, activities, and downloadable resources for future reference. There are required synchronous Live Zoom Events delivered via Zoom that are 1.5 hours each. Live Zoom Events will be moderated by a trained interventionist and will be tailored to the need of participants. Three Live Zoom Event are offered and participants are required to complete all three. Sections are opened once a month for ~3 months. The modules were developed by my research team, including undergraduate students and graduate students with a variety of academic backgrounds, in partnership with high school staff and other professionals specialize in LGBTQ+ youth or education. We use Canvas Learning Management Software to deliver PLANTS. We will monitor intervention compliance and fidelity via module guestionnaires, Canvas informatics, event attendance, and follow-up survey questionnaires.

